11.8 Interim Analysis

There are no interim analyses planned for this study.

12.0 DATA MANAGEMENT

12.1 Data Flow

Data generated by the BioStamp nPoint system and the reference devices, as well as data annotated on the CRFs, will be extracted and time-aligned by MC10 for entry into the trial database. During study execution, ground-truth data collected on CRFs and by reference devices will be stored at the study site. Data collected using BioStamp nPoint will be transmitted to the MC10 Cloud for processing and generation of analytic outputs. The process described below allows verification that the extraction and time-alignment processes do not introduce changes in the underlying data.

After the final subject has completed the study, the sum total of analytic outputs from the study will be exported from the MC10 Cloud and stored in a read-only archive. This archive will be entered into

MC10's Quality system, and a checksum to uniquely represent this archive will be computed. This checksum will be sent for entry into the trial database. After the checksum has been entered, CTI will archive all ground-truth data in a read-only format and compute a checksum on the resulting archive. This checksum will also be entered into the trial database. CTI will then send the ground-truth data archive to MC10 for data extraction and time-alignment. MC10 will then send the relevant data for entry into the trial database and subsequent analysis. All tools to be used in this process will be validated.

12.2 Data Collection

Data management will be performed by MC10 or their designee using a validated data system as specified in 21 CFR 11. Subject data will be entered into CRFs and combined with data provided from other sources in a validated data system that will reside in the clinical data management database.

Clinical data management will be performed in accordance with applicable MC10 or their designee's SOPs; data cleaning procedures will be performed with the objective of ensuring all data fields are populated, and removing errors and inconsistencies in the data which would otherwise impact the analysis and reporting objectives, or the credibility of the final study report.

The principal investigator is responsible for the accuracy and completeness of all study documentation. The clinical monitor will collect the originals and the investigational site shall retain the copies.

12.3 Data Processing

Visual and computer error checks will be carried out. The investigator will be queried on errors concerning completeness and consistency. Audits may be performed for quality assurance of data handling.

13.0 MONITORING AND QUALITY CONTROL PROCEDURES

13.1 Monitoring and Auditing

Sponsor personnel or their designees will monitor the study and verify subject data and ensure compliance with Good Clinical Practice (GCP), clinical protocol and other study requirements. Monitoring visits to the clinical site(s) will be made periodically during the study, to ensure that all aspects of the current, approved protocol/amendment(s) are followed.

Prior to the enrollment of any subject in this study, the Monitor and the Investigator will review the protocol, the procedure for obtaining informed consent and the procedure for reporting adverse events. On-site and remote monitoring visits will be performed by the Monitor. Case report forms will be verified against source documentation and subject compliance will be monitored.

The Monitor is responsible for ensuring, through personal contact with the Investigator and site personnel that the members of the clinical staff clearly understand and accept the obligations incurred in this investigation, and that these obligations are being fulfilled throughout the study. Specifically, the Monitor will interact with the site via telephone contact and periodic on-site visits to ensure that:

- Study facilities continue to be acceptable for the conduct of the study
- Regulatory and study documents are complete and up-to-date
- The protocol is appropriately followed
- Protocol amendments have been approved by the IRB and the local regulatory authorities (as applicable), and the Sponsor has received the approval in writing
- Qualified subjects are enrolled in a timely manner
- Accurate, complete, and current records are maintained for all subjects

- The information recorded and submitted to the Sponsor is representative of the subject record and other supporting documentation
- Problems with inconsistent and incomplete data are addressed
- Accurate, complete, and timely adverse event reports are being made to the Sponsor
- The Principal Investigator continues to assume primary responsibility for the study
- Investigational devices are properly stored, dispensed, and accounted for

13.2 Device Labeling

Labeling for the investigational devices will be limited to product labels and the Instructions for Use (IFU) for the operation of the device. The packaging of the BioStamp nPoint system will be labeled in compliance with 21 CFR Part 812.5. Each device label will include the wording “Caution – Investigational Device. Limited to Investigational Use” or similar language.

13.3 Device Accountability

Access to investigational devices shall be controlled and used only in the clinical investigation and according to the Protocol.

The Sponsor shall keep records to document the physical location of all investigational devices from shipment (or hand-carried) to the sites until return or disposal.

The principal investigator or an authorized designee shall keep records documenting the receipt, use, return, and disposal of the investigational device, which shall include:

- The date of receipt
- Identification of each investigational device (serial and or lot number)
- The date or dates of use
- Subject identification
- Date of return of unused, expired, or malfunctioning investigational device, if applicable

The Investigator must explain in writing the reasons for any discrepancy noted in device accountability.

14.0 ADVERSE EVENTS

14.1 Definitions

Adverse events will be recorded and documented throughout the duration of the study. In this study, adverse events will be defined and classified per ISO 14155:2011(E) Clinical Investigations of Medical Devices in Human Subjects - Good Clinical Practice and all applicable internal Sponsor procedures; see Table 12 for details. Per ISO 14155:2011(F), “ADE” will include any AE related to the investigational device, as well as any AE related to study design.

Table 12: Adverse Event Definitions

| Adverse Event | Non-device related | Device- or procedure-related | |
|---------------|-----------------------|---|---|
| Non-serious | Adverse Event | Adverse Device Effect (ADE) | |
| Serious | Serious Adverse Event | Serious Adverse Device Effect (SADE) | |
| | | Anticipated | Unanticipated |
| | | Anticipated Serious Adverse Device Effect | Unanticipated Serious Adverse Device Effect |

14.1.1 Adverse Events

Adverse events (AE) are any untoward medical occurrence, unintended disease or injury, or untoward clinical signs (including abnormal laboratory findings) in which subjects, users or other persons, whether or not related to the investigational medical device.

All adverse events, regardless of relationship to the device, must be recorded, as applicable, on the case report forms provided. Adverse events that occur during this study should be treated by established standards of care, which will protect the life and safety of the subjects.

Adverse events shall be assessed and documented at the time of the procedure and at all study follow-up visits. Each investigator shall provide source documentation as requested by the Sponsor to facilitate reporting and adjudication of these events.

14.1.2 Serious Adverse Events

An adverse event is considered a Serious Adverse Event (SAE) that

- a. led to death
- b. led to a serious deterioration in the health of the subject, that either resulted in
 - 1) a life-threatening illness or injury, or
 - 2) a permanent impairment of a body structure or a body function, or
 - 3) in - patient hospitalization or prolongation of existing hospitalization, or
 - 4) a medical or surgical intervention to prevent permanent life-threatening illness or injury or permanent impairment to body structure or a body function.
- c. led to fetal distress, fetal death or a congenital abnormality

14.1.3 Unanticipated Serious Adverse Device Effect

An Unanticipated Serious Adverse Device Effect (USADE) is defined as any serious adverse effect on health or safety or any life-threatening problem or death caused by, or associated with, a device, if that effect, problem, or death were not previously identified in nature, severity, or degree of incidence in the investigational plan or labeling, or any other unanticipated serious problem associated with a device that relates to the rights, safety, or welfare of subjects.

14.2 Adverse Event Reporting

Any adverse event that occurs during the course of the study must be reported using the appropriate form in the CRFs and the Investigator must sign each report. The Investigator must determine whether the adverse event is serious or unanticipated, its intensity, and the relationship of each adverse event to the investigational devices.

All serious adverse events, including unanticipated serious adverse device effects, must be reported within 24 hours of the site first becoming aware of the event using the appropriate CRF. All other adverse events (i.e. other than serious adverse events or unanticipated adverse device effects) must be recorded on the appropriate CRFs. The Medical Monitor will contact the site for additional information, if required.

For any adverse event that is ongoing at the time of the initial report, periodic follow-up information is required until the adverse event is resolved or is judged to be chronically stable. The site should submit relevant follow-up information related to the adverse event as soon as it is available.

Depending upon the nature and seriousness of the adverse event, the Medical Monitor may request the Investigator to provide copies of the subject's medical records (such as the subject's laboratory tests and hospital records, Investigator summaries, etc.) to document the adverse event. The Medical Monitor is available to respond to any medical issues that arise during the conduct of this

study.

The Investigator will report all serious adverse events, including unanticipated adverse device effects, to the IRB according to the IRB requirements. A copy of this IRB communication should be sent to the Sponsor.

Within 10 working days of notification, the Sponsor will report all unanticipated adverse device effects to the appropriate authority, all participating investigators, and all reviewing IRB. The Sponsor will ensure that safety reporting for the study is conducted in compliance with all pertinent requirements and regulations.

14.3 Adverse Event Reporting

14.3.1 Initial Assessment

The investigator must provide the following information:

- Date of onset
- Nature
- Severity
- Duration / date of resolution
- Outcome
- Relationship to investigational device
- Other relevant information

14.3.2 Assessment of Severity

The Investigator must determine the severity of the adverse event according to the following definitions:

- **Mild** - The adverse event is noticeable to the subject, but does not interfere with routine activity; the symptoms are easily tolerated and transient in nature.
- **Moderate** – The adverse event interferes with routine activity but responds to symptomatic therapy or rest; the symptoms are poorly tolerated and sustained.
- **Severe** – The adverse event significantly limits the subject's ability to perform routine activities despite symptomatic therapy. The adverse event requires medical or surgical treatment or results in hospitalization.
- **Life-Threatening** – **The subject is at immediate risk of death.**

14.3.3 Device Relatedness

The Investigator must provide an assessment of the adverse event association of device relatedness according to the following definitions:

- **Definite** – The adverse event is clearly related to the investigational device: the event has a temporal relationship to the investigational device, follows a known pattern of response, or is otherwise logically related to the investigational device, and no alternative cause is present.
- **Probable (Likely)** – The adverse event is likely related to the investigational device: the event has a temporal relationship to the investigational device, follows a known or suspected pattern of response, or is otherwise logically related to the investigational device, but an alternative cause may be present.
- **Possible (Unlikely)** – The adverse event is unlikely related to the investigational device: the event does not follow a clear temporal relationship to the investigational device or

does not follow a known pattern of response, or is otherwise likely to be due to the subject's clinical state or other modes of therapy.

- **Not Related** – The adverse event is clearly not related to the investigational device: the event has no temporal or other relationship to the administration of the investigational device follows no known or suspected pattern of response, and an alternative cause is present.
- **Unknown** – Unable to determine the relationship based on all available information.

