6.2 Schedule of Events

The evaluation period includes (refer to Section 4.1) clinician observed supervised testing. Subjects will wear a total of four BioStamp nPoint Sensors for this study; chest, thigh, shank, and forearm, and the BioStamp nPoint system will be configured, using only the chest and thigh Sensors, to measure and compute algorithm outputs.

In addition to the algorithm determinate Sensor locations, the shank and forearm Sensors (no sensor data will be collected) will be utilized in combination with the chest and thigh locations to validate the Sensor adhesion performance. The study is designed to capture supervised, observed measurements, as well as two nights of sleep in in clinic supervised setting.

Table 5: Schedule of Events

| Activities | Visit Day | Screening Period | Evaluation Period | | | | Safety Follow-Up |
|---|--------------|---------------------|-------------------|------------------|------------------|------------------|---------------------|
| | | 1 | Clinic 1 or 2 | Clinic 1 or 2 | Clinic 2 or 3 | Clinic 2 or 3 | Telephone |
| | | -60 to 0 | 0 | 1 | 1 | 2 | 3-5 |
| Screening & Enrollment Activities | | | | | | | |
| Informed Consent | | X | | | | | |
| Screening survey (demographics, medical history, etc.) | | X | | | | | |
| Baseline assessment (weight, Fitzpatrick, medical history, location irritation) | | X | X | | | | |
| Urine pregnancy and drug screen | | X | X | | | | |
| Sensor Application | | | | | | | |
| Application of Functional MC10 Sensors by Clinician | | | X | | | | |
| Application of Non-functional MC10 Sensors by Clinician | | | X | | | | |
| Adhesion application assessment | | | X | X | | | |
| Application of Functional MC10 Sensors by Subject | | | | X | | | |
| Application of Heart Rate Reference Device by clinician | | | X | | | | |
| Application of Respiration Reference Device for Sleep Respiration by clinician | | | X | | X | | |
| Prescribed Activities (Supervised) | | | | | | | |
| Activity Classification Activities | | | X | | | | |
| Heart Rate Activities | | | X | | | | |
| Subject training | | | | X | | | |
| Overnight sleep | | | X | | X | | |
| Prescribed Activities (Remote) | | | | | | | |
| | | | | X | | | |
| Time of Removal Assessments (MC10, Heart Rate Reference Device) | | | | | | | |
| Adhesion assessment | | | | X | | X | |
| Removal pain assessment | | | | X | | X | |
| Skin irritation assessment | | | | X | | X | |
| Sensor Removal | | | | | | | |

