11.6.3 Safety Analysis

Prior to analysis, all AEs will be coded using the MedDRA coding dictionary. Based on these coded terms, TEAEs will be summarized using system organ class and preferred terms, as well as by relationship to the study devices. All AEs will be listed, regardless of whether or not they were study treatment related.

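### Adverse events are graded for relatedness to the investigational device, but the ADE definition, the safety summary and the medical monitoring section each use a different relatedness target

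*Protocol*

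**What the plan says.** Section 14.2 has the investigator determine, for each adverse event, "its intensity, and the relationship of each adverse event to the investigational devices". Section 14.3.1 lists the items to be supplied, and its one relationship item names the investigational device. Section 14.3.3 then gives the scale, introduced by "The Investigator must provide an assessment of the adverse event association of device relatedness according to the following definitions". Four of its five grades are worded around the investigational device. The fifth, Unknown, names no device.

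The classification rests on something wider. Section 14.1 says that an ADE covers "any AE related to the investigational device, as well as any AE related to study design". Table 12 heads the column holding ADE and SADE "Device- or procedure-related", while the opposite column is for events not related to the device.

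The statistical section plans to summarise events by system organ class and preferred term, "as well as by relationship to the study devices". Section 5.0, titled Study Devices, covers the Actiheart and the Capnostream as well as the BioStamp nPoint system. Finally, Section 15.0 has the principal investigator decide whether an event was expected and whether the study itself was responsible.

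**The concern.** A category can be assigned reliably only if the judgement it depends on is asked for. Here the category uses one causal target and the graded judgement uses a narrower one. For an event that the sensor clearly did not cause but a study task did, the required grade points one way and the definition of an ADE points the other.

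What is at stake is the consistency of the ADE and SADE categories and the meaning of the 11.6.3 summary. This is a pivotal study for a 510(k) submission, so a clear separation of events due to the device from events due to other parts of the study is worth having. If a causality judgement is not recorded at the time of the event, it cannot be reliably rebuilt at analysis.

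**Working it through.** There is no figure to reproduce. The check sets the passages side by side.

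| Place in protocol | Relatedness target | Graded scale? | Listed data item? |
|---|---|---|---|
| 14.2, 14.3.1, 14.3.3 | Investigational device | Yes (14.3.3) | Yes (14.3.1) |
| 14.1 and Table 12 | Device, or procedure / study design | No | No |
| 11.6.3, read with 5.0 | Study devices, including the reference monitors | No | No |
| 15.0 | The study | No (yes/no) | No |

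Three hypothetical events, passed through these rules:

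1. **Skin reaction under a BioStamp sensor.** 14.3.3 gives a related grade, Table 12 gives ADE, and the event counts as related in 11.6.3. All agree.
2. **Fall during treadmill walking, in which the sensor played no part.** 14.3.3 gives Not Related, since another cause is present. Section 14.1 and the device-or-procedure column of Table 12 allow ADE. The event also fits Table 12's other column, because it is not device-related. Section 15.0 would call it study-related. The grade alone does not settle the category, and Table 12 admits both answers.
3. **Skin reaction under the Actiheart electrodes.** 14.3.3 gives Not Related, or Possible (Unlikely). In 11.6.3 the event is related to a study device if that term has its Section 5.0 meaning, yet no listed item records this. Whether Table 12 makes it an ADE depends on whether wearing a reference device counts as procedure or study design. The protocol does not say.

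The exposures behind cases 2 and 3 are part of the planned schedule:

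- Table 7, walking and biking: (6 × 5) + (1 × 5) + (8 × 5) = 30 + 5 + 40 = 75 minutes per subject.
- Table 7, leaning: 4 standing and 4 sitting leans, 1 minute each, 5 repetitions: 8 × 1 × 5 = 40 minutes.
- Table 8, treadmill and recumbent bike: at least 2 × 22 minutes of each, so 2 × 2 × 22 = 88 minutes.
- The Actiheart goes on at Day 0 and comes off on Day 2 (Table 5, Section 8.10.5). The nasal cannula is worn on two nights.

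Table 5 also places the removal-pain and skin-irritation rows under a heading that names the heart rate reference device, so effects at that device are foreseen. These figures measure exposure. They do not estimate how many events would be misclassified.

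**The case against.** The strongest reply is that the wider judgement is not absent. Section 15.0 requires a decision on relatedness to the study, and that could move a treadmill fall into the ADE column. The CRF is not shown and may carry further fields. Section 14.3.1 also collects the nature of the event and other relevant information, and Section 14.1.1 provides for source documents to support adjudication. Most of this stands. It means that events *can* be classified inconsistently, not that they will be. But Section 15.0 gives no scale, no listed item and no link to Table 12. A SAP can define a table, but it cannot supply a judgement that nobody recorded.

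A reader might go further and infer that a serious procedure-related event graded Not Related would escape the unanticipated-event route. The text does not support that. Section 14.2 has the investigator judge whether an event is serious or unanticipated, and requires every SAE to be reported within 24 hours whatever its relatedness. The definition in Section 14.1.3 is not tied to a 14.3.3 grade.

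A reader might also infer that the sensor's irritation profile is biased by reactions under the reference electrodes. Irritation is scored after sensor removal on its own scale (Table 9), with Section 8.10.4 specifying the sensor locations. That scoring does not pass through the adverse-event grade.

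Nor do the documents say outright that reference-device events are ADEs. That is a reasonable reading of procedure or study design, but neither Section 14.1 nor Table 12 names those devices.

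**Conclusion.** The point holds as an internal inconsistency. Four relatedness targets are in use, and only the investigational device has both a graded scale and a listed data item. The ADE/SADE category and the 11.6.3 summary cannot be derived from that grade, and Table 12's two columns overlap for an event caused by a procedure but not by the device. Events from the exercise and leaning tasks are the clear case; reference-device events are an arguable one.

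The size cannot be put as a number. The protocol gives no expected adverse-event frequency and specifies no ADE rate, so a percentage-point shift in such a rate would have nothing to refer to. SAE reporting and the accuracy and adhesion results are untouched. The conclusion assumes that the listed items in Section 14.3.1 reflect what is collected, and that the term study devices in 11.6.3 has its Section 5.0 meaning. If the CRF already records procedure and reference-device relatedness, only the wording needs correcting.

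**What to change.** Reconcile Sections 11.6.3, 14.1 with Table 12, 14.2, 14.3.1, 14.3.3 and 15.0:

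- In 14.2, 14.3.1, 14.3.3 and the adverse-event CRF, record relatedness separately for (a) BioStamp nPoint, (b) the reference devices and (c) study procedures.
- In 14.1, state which of (a), (b) and (c) make an event an ADE or SADE, and say explicitly whether (b) counts.
- Reword Table 12's columns so that an event caused by a procedure but not by the device fits only one of them.
- In 15.0, say how the study-relatedness judgement is recorded and how it feeds Table 12.
- In 11.6.3, tabulate (a), (b) and (c) separately.

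The cost is two extra CRF fields and one extra table breakdown, with no added visits or procedures.
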